3.3 DOSE ESCALATION

Dose escalation will proceed according to the following schedule (**Table 4**) and guidelines (**Table 5**). Dose-limiting toxicity (DLT) is defined above. Each patient will continue treatment at the dose level they were enrolled — there will be no intra-patient dose escalation.

The MTD is the dose level at which no more than 1 of up to 6 patients experience DLT during the DLT evaluation window(s), or the dose below that at which at least 2 (of \leq 6) patients have DLT. If a patient did not experience a DLT and did not finish treatment during the DLT window, he or she will not be evaluable for toxicity and will be replaced in that dose level. The protocol will be amended to note the MTD once determined.

Table 4: IL-15 Dose Escalation Schedule

Dose Level	rhIL-15 (all cycles) (mcg/kg/day)	Obinutuzumab** (mg)
Level 1	0.5 on day 1-5	1000
Level 2	1 on day 1-5	1000
Level 3	2 on day 1-5	1000

^{*}Doses are stated as exact dose in units (e.g., mg/m², mcg/kg, etc.) rather than as a percentage.

Table 5: Dose Escalation Guidelines

Number of Patients with DLT at a Given Dose Level	Escalation Decision Rule
0 out of 3	Enter 3 patients at the next dose level.
≥2	Dose escalation will be stopped. This dose level will be declared the maximally administered dose (highest dose administered). Three (3) additional patients will be entered at the next lowest dose level if only 3 patients were treated previously at that dose.

^{**} Each dose of obinutuzumab is 1000mg IV on day 4, with the exception of infusions in Cycle 1, which are administered on day 4 (100 mg) and day 5 (900 mg), day 11 (1,000 mg) and day 18 (1,000 mg).

Version Date: 09/14/2021

Number of Patients with DLT at a Given Dose Level	Escalation Decision Rule
1 out of 3	 Enter at least 3 more patients at this dose level. If 0 of these 3 patients experience DLT, proceed to the next dose level. If 1 or more of this group suffer DLT, then dose escalation is stopped, and this dose is declared the maximally administered dose. Three (3) additional patients will be entered at the next lowest dose level if only 3 patients were treated previously at that dose.
≤1 out of 6 at highest dose level below the maximally administered dose	This is generally the recommended Phase II dose. At least 6 patients must be entered at the recommended Phase II dose.

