National Institutes of Health (NIH)-funded investigators and clinical trial site staff who are responsible for the conduct, management, or oversight of NIH-funded clinical trials have completed Human Subjects Protection and ICH GCP Training.

The protocol, informed consent form(s), recruitment materials, and all participant materials will be submitted to the Institutional Review Board (IRB) for review and approval. Approval of both the protocol and the consent form must be obtained before any participant is enrolled. Any amendment to the protocol will require review and approval by the IRB before the changes are implemented to the study. In addition, all changes to the consent form will be IRB-approved; an IRB determination will be made regarding whether a new consent needs to be obtained from participants who provided consent, using a previously approved consent form.

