10.2 SAMPLE SIZE DETERMINATION

The MTD will be based on the assessment of DLT during the first cycle of treatment and will be defined as the dose level at which less than one-third of patients (0 of 3 or 0-1/6 patients) treated experience a DLT, with the next higher dose level demonstrating one-third or a greater number of patients ($\geq 2-3$ or $\geq 2-6$ patients) having a DLT. If a subject did not experience a DLT and did not finish one cycle of treatment (28 days) he or she will not be evaluable for determination of the MTD and would be replaced in the dose level. An additional 3 to 6 patients will be enrolled at the MTD, so that a total of 9 patients will be treated at this dose.

Using this dose-escalation scheme the probability of escalating to the next dose level will be based on the true rate of DLT at the current doses given by the following table (each group will be

Version Date: 09/14/2021

considered independently of the other); Thus, if the true underlying proportion of DLTs is 50% at the current dose there is a 17% probability of escalating to the next dose.

True toxicity at a given dose	10%	20%	30%	40%	50%	60%
Probability of escalating	0.91	0.71	0.49	0.31	0.17	0.08

If all three dose levels are evaluated with 6 patients per dose level and 9 total patients at the MTD, a maximum of 21 evaluable patients will be enrolled. To account for non-evaluable patients, accrual ceiling will be set at 24 patients. Similarly, if all dose levels are evaluated with 3 patients per dose level and 9 total patients at the MTD, the minimum number of evaluable patients required will be 12. It is expected that the accrual can be completed in 24 months.

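### The second limb of the MTD definition in 3.3 sets no DLT limit at the dose it names, so it can name a re-opened level with 2/6 or 3/6 DLTs that 10.2 excludes

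*Combined protocol and SAP*

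**What the plan says.** Section 3.3 (Dose Escalation) gives two alternative ways for a dose to be the MTD. The first limb reads "The MTD is the dose level at which no more than 1 of up to 6 patients experience DLT". The second limb follows in the same sentence: "experience DLT during the DLT evaluation window(s), or the dose below that at which at least 2" of at most 6 patients have DLT.

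Section 10.2 (Sample Size Determination) gives a different definition. The MTD is "defined as the dose level at which less than one-third of patients (0 of 3 or 0-1/6 patients) treated experience a DLT", and the next higher level must show DLTs in one-third or more. Both conditions apply together.

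Table 5 in 3.3 supplies the path between the two. After 0 of 3 DLTs the instruction is "Enter 3 patients at the next dose level". When a level is stopped for DLTs, "Three (3) additional patients will be entered at the next lowest dose level if only 3 patients were treated previously at that dose". The last row of Table 5 asks for at most 1 of 6 at the recommended Phase II dose, but qualifies this with 'generally' and does not mention the MTD.

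Table 4 lists three rhIL-15 levels (0.5, 1 and 2 mcg/kg/day) and none below 0.5. Section 10.2 then expands at the MTD "so that a total of 9 patients will be treated at this dose". Section 3.3 adds that "The protocol will be amended to note the MTD once determined", and the Statement of Compliance says "Any amendment to the protocol will require review and approval by the IRB before the changes are implemented to the study".

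**The concern.** The second limb of 3.3 looks only at the dose above. A level cleared at 0/3 and later re-opened can collect 2 or 3 DLTs among its three added patients. It is still the dose below a toxic one, so 3.3 names it as MTD. Section 10.2 does not, because 2/6 and 3/6 are not less than one-third.

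The MTD is a primary endpoint (10.1) and sets the dose for Arm 2 (2.3.1.2). If the 3.3 wording were joined to the expansion to 9, three more patients would enter a dose at which one-third or one-half of 6 had had a DLT. When the re-opened level is level 1, no lower level exists, and no text says that the outcome is 'no MTD'.

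**Working it through.** **Inputs.** Escalation and re-opening rules: Table 5. Levels: Table 4. Escalation probabilities: 10.2. True DLT rates for the combination are not in the documents, so those below are assumptions. Write p1, p2, p3 for the rates at levels 1 to 3.

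**Step 1: reproduce the plan's figure.** The probability of escalating is E(p) = (1−p)³ + 3p(1−p)² × (1−p)³. At p = 50%: 0.125 + 0.375 × 0.125 = 0.172, against 0.17 stated. At 10% to 60%, E = 0.906, 0.709, 0.494, 0.309, 0.172 and 0.082. The table in 10.2 gives 0.91, 0.71, 0.49, 0.31, 0.17 and 0.08. All six agree, so Table 5 is being read as the plan intends.

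**Step 2: possible counts at a re-opened level.** A level left with only 3 patients was left at 0/3. After three more it stands at 0/6, 1/6, 2/6 or 3/6. The chance of 2/6 or 3/6, given re-opening, is R(p) = 3p²(1−p) + p³, which is 0.028, 0.104 and 0.216 at 10%, 20% and 30%.

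**Step 3: what each text names.**

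| End state | Second limb of 3.3 | 10.2 |
|---|---|---|
| (a) Level 2 re-opened to 2/6 or 3/6, level 1 at 0-1/6 | Level 2 (below level 3), and also level 1 (below level 2) | Level 1 only |
| (b) Level 1 re-opened to 2/6 or 3/6 | Level 1 (also level 2, if that was re-opened first) | No dose |

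In (a), the row of Table 5 for two or more DLTs also sends the trial down to level 1. In (b) there is nowhere lower to go.

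**Step 4: how often.**

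- P(b) = (1−p1)³ × [(1−E(p2)) + (1−p2)³(1−E(p3))R(p2)] × R(p1)
- P(a) = (1−p2)³(1−E(p3))R(p2) × [3p1(1−p1)⁵ + (1−p1)³(1−R(p1))]

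Example for (b) at 20/35/50%: 0.512 × [0.6035 + 0.2746 × 0.8281 × 0.2818] × 0.104 = 0.512 × 0.6676 × 0.104 = 0.0355.

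| Assumed rates, levels 1/2/3 | (b) conflict | (a) settled elsewhere |
|---|---|---|
| 10/20/30% | 0.65% | 2.4% |
| 10/25/45% | 0.92% | 4.5% |
| 10/30/60% | 1.2% | 6.0% |
| 10/40/60% | 1.6% | 6.2% |
| 20/30/40% | 3.0% | 3.4% |
| 20/35/50% | 3.6% | 4.2% |
| Flat 10% | 0.2% | 0.2% |
| Flat 20% | 1.6% | 1.0% |
| 5/10/20% | 0.06% | 0.6% |

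Case (b) depends mainly on p1. With level 1 as high as 30% (30/40/50%) it would be 0.343 × [0.6907 + 0.216 × 0.8281 × 0.352] × 0.216 = 5.6%.

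**Step 5: first entry at level 1.** The chance that level 1 is stopped at first entry is 1 − E(p1): 9.4% at 10% and 29.1% at 20%. There the second limb has no dose below to name and 10.2 names none, so the two definitions agree, though neither states the outcome.

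**Step 6: check of the proviso.** With at most 1 of 6 DLTs required at the lower dose, the second limb asks for the same two facts as 10.2. It then names level 1 only in (a) and no dose in (b). Over every path on the first eight curves in the table, the probability that it disagrees with 10.2 is zero.

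**The case against.** The strongest reply is that 3.3 should not be read alone.

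- Taken by itself, the first limb would name every cleared level, so the sentence plainly relies on Table 5 and 10.2 to select a dose. This is right, and it disposes of case (a). It does not dispose of (b), where reading the texts together leaves 3.3 naming level 1 and 10.2 naming nothing.
- A reader might infer that the protocol directs three more patients to a toxic dose. The documents do not support this. Section 3.3 has no expansion rule. The expansion count is in 10.2, directly after the definition that excludes 2/6 and 3/6.
- A reader might also take 3.3 as the governing definition. No text ranks it above 10.2.
- If no dose meets 10.2, it can fairly be said that there is no MTD. That is the sensible reading, but 3.3 still says otherwise in its own words.
- Level 1 may be well tolerated. In the 10-day continuous-infusion monotherapy trial (1.2.10.2) the DLTs were at 4.0 mcg/kg/day and 2.0 was the MTD. Level 1 here is 0.5 for 5 days, and a first grade 3 obinutuzumab infusion reaction is exempt (3.2.2). This favours the lower figures, but does not settle the rate for an untested combination.

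Weekly team review (7.4.1), the suspension clause (13.1) and the IRB-approved amendment are real safeguards. They are not a rule for declaring the MTD.

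**Conclusion.** The point holds as a contradiction in the wording of a primary endpoint, with small practical risk. The second limb of 3.3 admits a re-opened level at 2/6 or 3/6, and 10.2 excludes it. Only a re-opened level 1 is left in direct conflict: about 0.7-3.6% of trials on the six rising curves with level 1 at 10-20%, and 0.06% at 5/10/20%. These figures rest on assumed DLT rates and independent patients. They count how often the conflicting state arises, not how often a wrong dose would be chosen.

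Adding (a) to (b) gives 3.0-7.8% on the same six curves, and a reader might take that as the size of the defect. It is not, because Table 5 and 10.2 already resolve (a). The text conflict itself does not depend on any assumed rate, and it is best settled before DLT data exist.

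**What to change.** Make two edits in 3.3.

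1. Add to the end of the second limb: 'provided no more than 1 of 6 evaluable patients has a DLT at that lower dose'. This edit brings the limb into agreement with 10.2.
2. As a clarification, add: 'If 2 or more of the first up to 6 evaluable patients at level 1 have a DLT, at first entry or after re-opening, no MTD is declared and no expansion is enrolled unless a lower level is added by amendment.'

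The denominator in the second edit keeps later DLTs among the 9 expansion-stage patients from voiding an MTD already declared. The amendment clause leaves room for a lower level, such as the 0.25 mcg/kg/day given in the earlier trials (1.2.10.1 and 1.2.10.2). For first entry, the sentence only writes down what both definitions already imply.

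The cost is one clause and one sentence. Table 5, the expansion to 9 patients, the evaluable maximum of 21 (6 + 6 + 9), the ceiling of 24 and the escalation-probability table do not change.

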3.4 DRUG ADMINISTRATION

Each cycle of treatment is 28 days (4 weeks). The minimum window between initiation of new cycles is 26 days; a cycle delay due to scheduling or other administrative reasons (i.e., reasons other than toxicity/dose management as defined below) is 7 days.

Treatment will be administered on an inpatient basis during week 1 of the first cycle, and as outpatient during subsequent weeks and cycles unless decided otherwise by the principal investigator based on clinical judgment. Reported adverse events and potential risks are described in Section 14. Appropriate dose modifications are described in Section 3.5. No investigational or commercial agents or therapies other than those described below may be administered with the intent to treat the patient's malignancy.

		Regimen l	Description	
Agent	Premedications; Precautions	Schedule	Dose	Route
rhIL-15	Premedicate with acetaminophen and/or ibuprofen	Cycles 1-6 Days 1-5	** in *** mL D5W with 0.1% HSA	IV over 24 hours
		Cycle 1 Day 4	** in 100 mL NS	IV at 25 mg/hr over 4 hours
Obinutuzumab	Infusion reaction and tumor lysis	Cycle 1 Day 5	** in 250 mL NS	IV at 50 mg/hr (if no infusion reaction during prior infusion) OR 25 mg/hr (if an infusion reaction occurred during prior infusion); may escalate in increments of up to 50 mg/hr every 30 minutes to a maximum rate of 400 mg/hr
Oomatazamao	syndrome prophylaxis*	Cycle 1 Day 11	** in 250 mL NS	If no infusion reaction occurred during the previous infusion and
		Cycle 1 Day 18	** in 250 ml NS	the final infusion rate was 100 mg/hr or faster, IV infusions can be started at a rate of 100 mg/hr and
		Cycles 2-6 Day 4	** in 250 mL NS	increased by 100 mg/hr increments every 30 minutes to a maximum of 400 mg/hr. If an infusion reaction occurred

Version Date: 09/14/2021

		Regimen l	Description	
Agent	Premedications; Precautions	Schedule	Dose	Route
				during the previous infusion, administer IV at 50mg/hr. The rate of infusion can be escalated in increments of 50mg/hr every 30 minutes to a maximum rate of 400mg/hr.

^{*}See Section 3.4.2.

Infusions may be done peripherally or via central venous access device (if present; not required to be placed by the study). When administered on an outpatient basis, rhIL-15 will be infused via an ambulatory infusion pump. On days that both rhIL-15 and obinutuzumab are given together (i.e., Day 4 and 5 of Cycle 1, and Day of of each subsequent Cycle), rhIL-15 infusion will be held up to two hours prior to, and up to two hours following the obinutuzumab infusion.

3.4.1 Prophylactic and Supportive Care for rhIL-15

Patients will be given acetaminophen 500-650 mg IV or orally 30 to 60 minutes prior to each IL-15 infusion as first line, and ibuprofen 400 mg or 600 mg orally depending on reactions with acetaminophen as a premedication

3.4.2 Prophylactic and Supportive Care for Obinutuzumab

As hypotension may occur during obinutuzumab infusions, antihypertensive treatments may be held for 12 hours prior to and throughout each obinutuzumab infusion and for the first hour after administration.

Premedication to reduce the risk of infusion reactions is outlined below.

Premedication	for obinutuzumab in	nfusion to reduce infusion-re	elated reactions (IRR)
Day of treatment cycle	Patients requiring premedication	Premedication	Administration
Cycle 1, Day 4		IV glucocorticoid: 20 mg dexamethasone OR 80mg methylprednisolone	Completed at least 1 hour prior to obinutuzumab infusion
AND Cycle 1, Day 5	All patients	650-1000 mg acetaminophen	At least 30 minutes
Cycle 1, Day 3		Anti-histamine (e.g., 50 mg diphenhydramine)	before obinutuzumab infusion
All subsequent	All patients	650-1000 mg acetaminophen	At least 30 minutes before obinutuzumab infusion
infusions	Patients with an IRR	650-1000 mg acetaminophen	At least 30 minutes
	(Grade 1-2) with prior infusion	Anti-histamine (e.g., 50 mg diphenhydramine)	before obinutuzumab infusion

^{**}Doses as appropriate for assigned dose level.

^{***} Infusion volume of rhIL-15 per calculation in APPENDIX C: IL-15 Dilution Instructions

Version Date: 09/14/2021

Premedication	for obinutuzumab in	nfusion to reduce infusion-re	elated reactions (IRR)
Day of treatment cycle	Patients requiring premedication	Premedication	Administration
	Patients with a grade 3 IRR with the previous infusion OR	IV glucocorticoid: 20 mg dexamethasone OR 80mg methylprednisolone	Completed at least 1 hour prior to obinutuzumab infusion
	ALC > 25 X 10 ⁹ /L prior to next treatment	650-1000 mg acetaminophen Anti-histamine (e.g., 50 mg diphenhydramine)	At least 30 minutes before obinutuzumab infusion

As the effects of combined treatment with rhIL-15 and obinutuzumab in CLL are unknown, all patients on the protocol will receive tumor lysis syndrome prophylaxis during Cycle 1. They will be premedicated with anti-hyperuricemics (e.g., allopurinol or rasburicase) at least 24 hours prior to each obinutuzumab infusion, with adequate hydration ensured. Prophylaxis will be continued for each subsequent cycle in patients with high tumor burden, ALC $> 25 \times 10^9$ /L, and renal impairment (creatinine $> 1.5 \times 10^9$ /L)

3.4.3 Antimicrobial Prophylaxis

Patients with Grade 3 to 4 neutropenia lasting more than one week will receive antimicrobial prophylaxis until resolution of neutropenia to Grade 1 or 2. Antiviral and antifungal prophylaxis will be considered in patients with history of viral and fungal infections.

3.4.4 Other Modalities or Procedures

Patients will be observed in the day hospital or the inpatient unit for at least 60 minutes after administration of obinutuzumab for potential infusion-related reactions.

Patients with Grade 3-4 neutropenia may receive granulocyte colony-stimulating factor until ANC \geq 5 X 10⁹ /L.

3.5 ASSESSMENT OF SAFETY AND DOSE MODIFICATIONS

3.5.1 rhIL-15-specific Adverse Events

Please refer to the Comprehensive Adverse Event and Potential Risk list (CAEPR) for rhIL-15 presented in Section 14.1.8.

Dose of rhIL-15 is based on the dose level and patient's weight at the beginning of each cycle, and can only be modified for rounding and/or consistency with prior cycles, and not for adverse events or renal/hepatic dysfunction. Infusion may continue during correction of electrolyte and other laboratory abnormalities listed in Section 3.2. Infusion may be interrupted for other reasons for up to two hours each day (in addition to interruptions due to administration of obinutuzumab) but treatment should end $120 \, (\pm 1)$ hours after initiation on Day 1.

3.5.2 Obinutuzumab-specific Adverse Events

Important risks identified in clinical investigations with obinutuzumab were: IRRs, TLS, thrombocytopenia (including acute thrombocytopenia), neutropenia (including prolonged and late onset neutropenia), prolonged B-cell depletion, infections (including hepatitis B reactivation and PML), worsening of pre-existing cardiac conditions GI perforation, and secondary malignancies. Obinutuzumab dose may be held as specified below, but not otherwise modified.

Version Date: 09/14/2021

3.5.2.1 Hepatitis B Reactivation

HBV reactivation, in some cases resulting in fulminant hepatitis, hepatic failure, and death, can occur in patients treated with anti-CD20 antibodies such as obinutuzumab. HBV reactivation has been reported in patients who are HBsAg positive and also in patients who are HBsAg negative but are anti-HBc positive. Reactivation has also occurred in patients who appear to have resolved hepatitis B infection (i.e., HBsAg negative, anti-HBc positive, and hepatitis B surface antibody [anti-HBs] positive). HBV reactivation is defined as an abrupt increase in HBV replication manifesting as a rapid increase in serum HBV DNA level or detection of HBsAg in a person who was previously HBsAg negative and anti-HBc positive. Reactivation of HBV replication is often followed by hepatitis, i.e., increase in transaminase levels and, in severe cases, increase in bilirubin levels, liver failure and death.

All patients will be screened for HBV infection by measuring HBsAg and anti-HBc before initiating treatment with obinutuzumab. As noted in Section 2.1.2.7, patients who show evidence of hepatitis B infection (HBsAg positive [regardless of antibody status] or HBsAg negative but anti-HBc positive) will be excluded from the study due to to the risk of HBV reactivation.

3.5.2.2 Progressive Multifocal Leukoencephalopathy (PML)

JC virus infection resulting in PML, which can be fatal, was observed in patients treated with obinutuzumab. Consider the diagnosis of PML in any patient presenting with new onset or changes to preexisting neurologic manifestations. Evaluation of PML includes, but is not limited to, consultation with a neurologist, brain magnetic resonance imaging and lumbar puncture. Discontinue obinutuzumab therapy and consider discontinuation or reduction of any concomitant chemotherapy or immunosuppressive therapy in patients who develop PML.

3.5.2.3 Infusion-Related Reactions (IRRs)

Obinutuzumab can cause severe and life-threatening IRRs; 65% of patients with CLL experienced a reaction to the first 1000 mg infused of obinutuzumab, and 38% of iNHL patients experienced a reaction on Day 1 of obinutuzumab infusion. IRRs within 24 hours of receiving obinutuzumab have occurred. IRRs can also occur with subsequent infusions. Symptoms may include hypotension, tachycardia, dyspnea, and respiratory symptoms (e.g., bronchospasm, larynx and throat irritation, wheezing, and laryngeal edema). Most frequently reported symptoms include nausea, fatigue, dizziness, vomiting, diarrhea, hypertension, flushing, headache, pyrexia, and chills

If a patient experiences an infusion reaction during obinutuzumab infusion, adjust the infusion as follows:

- **Grade 4 (life-threatening):** Stop all infusions immediately and permanently discontinue protocol therapy.
- **Grade 3 (severe):** Interrupt all infusions and manage symptoms. Upon resolution of symptoms, restart rhIL-15 infusion at prior rate, consider restarting obinutuzumab infusion at no more than half the previous rate (the rate being used at the time that the infusion reaction occurred) and, if patient does not experience any further infusion reaction symptoms, obinutuzumab infusion rate escalation may resume at the increments and intervals as appropriate for the treatment cycle dose (the Cycle 1 Day 4 infusion rate may be increased back up to 25 mg/hr after 1 hour but not increased further). Permanently discontinue treatment if patients experience a Grade 3 infusion-related symptom at rechallenge.

Version Date: 09/14/2021

• **Grade 1-2 (mild to moderate):** Reduce obinutuzumab infusion rate or interrupt obinutuzumab infusion and treat symptoms. Upon resolution of symptoms, continue or resume infusion and, if patient does not experience any further infusion reaction symptoms, infusion rate escalation may resume at the increments and intervals as appropriate for the treatment cycle dose (the Day 1 infusion rate may be increased back up to 25 mg/hr after 1 hour but not increased further).

